9.6.2.2. Classification of outcomes (Amended 05 October 2017)

This Registry uses the term 'birth defects' for outcomes sometimes referred to as 'congenital anomalies'. For purposes of analysis, pregnancy outcomes are dichotomized according to the presence or absence of birth defects. ***Pregnancy outcomes are*** further categorized as: 1) live births, 2) spontaneous abortions (i.e., pregnancy losses), 3) ***Elective/induced abortions*** and 4) ***Fetal deaths/Stillbirths***.

This Registry adopts a definition of a child with a birth defect as any live or stillborn neonate with a structural or chromosomal abnormality diagnosed before 6 years of age. The Registry employs a conservative approach of including all morphologic anomalies, including minor ones, as birth defects.

To provide consistency in the definitions of major defects in this Registry, CDC MACDP criteria are used for the classification of defects [CDC, 2008; Correa-Villasenor, 2003]. Some of the conditions excluded from the MACDP criteria for major structural defects may actually have major clinical, functional, or genetic significance. Therefore, minor malformations not appearing in the CDC inclusion list may be classified as birth defects in this Registry. In addition, CDC guidelines disqualify as defects those findings that are present in infants delivered at less than 36 weeks of gestation and are attributable to prematurity itself, such as a patent ductus arteriosus or inguinal hernias. Infants with infectious conditions (e.g., neonatal sepsis) or isolated biochemical abnormalities (e.g., hyperbilirubinemia) are classified as being without birth defects unless there is a possibility that the condition reflects an unrecognized congenital abnormality. All other congenital abnormalities are included in the 'birth defects' category, regardless of whether the neonate is delivered alive, including structural defects in neonates delivered prior to 20 weeks of gestation or weighing less than 500 g.

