definition and prospective ascertainment, reports a frequency of 5% to 7% [Chung, 1975]. Most major structural defects originate during the first trimester of pregnancy, which is the critical time for organogenesis [CDC, 2013b]. For such defects, exposures occurring in the second or third trimester are not likely to be causally associated. However, for the sake of completeness and to enable the assessment of possible increases in the frequency of birth defects, all defects will be included in the periodic summary reports of this Registry.

Criteria for review of a specific individual report include:

- Is the timing of the vaccination with *Boostrix* commensurate with the ontogenetic development of the organ(s) affected by the abnormalities?
- Is there another known or likely cause (e.g., pre-existing genetic or chromosomal defect or exposure to a known teratogen)?
- Is the congenital abnormality not previously described (i.e., is it new to medical science)?
- Is there a unique constellation of defects (i.e., is there a new syndrome)?

Criteria for review of aggregate data include:

- Is there a deviation from the expected frequency of all defects indicating an increase in the overall risk of defects?
- Is there a deviation from the expected frequencies of individual defects?
- Is there uniqueness (e.g., a pattern) of the abnormalities that is suggestive of a common etiology?

Studies have shown that the risk of spontaneous abortion is high early in pregnancy and decreases substantially from week 8 to week 28, yielding a cumulative estimated risk of 10% to 22% [Wilcox, 1981; Wilcox, 1983; Wilcox, 1988; Fenster, 1997; Windham, 1997; Khattak, 1999; Anderson, 2000; Osborn, 2000].

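### Section 9.6.2.2 leaves off-list minor malformations optional in the birth-defect numerator, and no described step fixes the defect call before vaccination timing is considered

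*Combined protocol and SAP*

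**What the plan says.** Section 9.6.2.2 (Classification of outcomes) contains these rules, in this order:

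- An inclusive rule: "The Registry employs a conservative approach of including all morphologic anomalies, including minor ones, as birth defects".
- A standard for major defects: "To provide consistency in the definitions of major defects in this Registry, CDC MACDP criteria are used for the classification of defects".
- A permissive rule, drawn as a consequence of the remark that some conditions excluded by the CDC criteria may be important: "minor malformations not appearing in the CDC inclusion list may be classified as birth defects in this Registry".
- A rule for infectious conditions and isolated biochemical abnormalities, which "are classified as being without birth defects unless there is a possibility that the condition reflects an unrecognized congenital abnormality".
- A closing catch-all: "All other congenital abnormalities are included in the 'birth defects' category, regardless of whether the neonate is delivered alive".

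Section 9.7 (Data analysis) uses this classification as the numerator of the birth-defect risk: infants with a defect over all infants. It stratifies outcomes by trimester of exposure, with a further preconception stratum, and sets them against external rates. It provides for no confidence intervals.

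Section 9.7 also lists questions for the review of an individual report. The first asks whether the timing of vaccination is "commensurate with the ontogenetic development of the organ(s) affected by the abnormalities". Another asks about alternative causes.

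The protocol does not say who makes the defect call, in what order the steps are taken, or whether the vaccination date is visible at that point. The ENCePP checklist in Annex 2 (item 11.5) answers No on independent review of study results.

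**The concern.** A mandatory rule and a permissive rule cover the same findings. Someone who reads *all* and someone who reads *may* can both follow the protocol and still count differently. The permissive sentence follows from the point that some excluded conditions have real significance, which can be read as an invitation to select the significant ones.

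Two things are at stake. The first is the pooled risk, which is compared with an external rate as a point estimate. A numerator that depends on who classified the case weakens that comparison.

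The second is the trimester pattern. Section 9.7 states that exposure after the first trimester is an unlikely cause of most major structural defects. Someone who holds that expectation and can see the vaccination date might resolve borderline findings differently by trimester. Nothing in the plan says that this happens, and nothing in it prevents it.

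**Working it through.** **Inputs**

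- Classification sentences: Section 9.6.2.2, as quoted above.
- Risk formula, strata, and background rates of about 3% (1 of 33) under CDC criteria and 5% to 7% under a broader definition: Section 9.7.
- 391 prospective reports from 03 May 2005 to 02 August 2013, and fewer than 100 registrations a year expected: Section 9.2.1.2.
- No minimum sample size: Section 9.5.
- My assumptions: 391 infants with known outcome (generous for that period, since it ignores loss to follow-up; later accrual is also ignored), and round figures of 200 and 100.

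**1. The plan's own figure.** 1/33 = 3.03%, which agrees with the stated 3%. The plan has no sample size, power or test to reproduce.

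**2. Which findings are left to judgement**

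| Finding | Governing text | Discretion |
|---|---|---|
| Defect meeting CDC MACDP criteria | Stated criteria | None from this wording |
| Minor malformation off the CDC list | *All* in one paragraph, *may* in the next | Yes: no criterion for *may* |
| Infectious or isolated biochemical condition | Not a defect unless a *possibility* exists | Yes: no threshold |
| Any other congenital abnormality | Catch-all, included | None |

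Judgement therefore touches part of the numerator, not all of it.

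**3. Effect of discretionary calls on the risk.** Counting or not counting *m* findings among *n* infants moves the risk by 100 × *m*/*n* percentage points. For *m* = 4:

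- *n* = 391: 400/391 = 1.02 points
- *n* = 200: 400/200 = 2.0 points
- *n* = 100: 400/100 = 4.0 points

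**4. Differential calls by trimester (hypothetical).** Take two strata of 100 infants, each with the same number of listed defects and four off-list minor findings. If the four are counted in one stratum and not in the other, a gap of 4/100 = 4 percentage points appears where none exists. This shows the mechanism only. The protocol gives no stratum sizes and no frequency of off-list findings.

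**5. Illustrative ceiling from case definition.** Expected counts *n* × *p*:

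| *n* | 3% | 5% | 7% |
|---|---|---|---|
| 391 | 11.7 | 19.6 | 27.4 |
| 200 | 6 | 10 | 14 |
| 100 | 3 | 5 | 7 |

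The ratios are 5/3 = 1.67 and 7/3 = 2.33, and the difference is 2 to 4 percentage points. Section 9.7 attributes variation among such estimates to populations and ascertainment as well as case definition, and it describes the higher figure as prospectively ascertained. The whole gap therefore cannot be assigned to the *may* sentence.

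**6. Order of steps.** The timing question in Section 9.7 concerns reports in which abnormalities are already identified, so it belongs to signal review. No text requires the defect call to be recorded before that review, or made without the vaccination date.

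**The case against.** The best answer is that the section is inclusive when read whole. The *may* sentence lies between a rule that takes in all morphologic anomalies and a catch-all that takes in everything else. On that reading, *may* means *can*: absence from the CDC list does not disqualify a finding. Section 9.7 and the abstract add that all defects go into the periodic reports whatever the trimester, so implausible timing is no ground for omission. Much of this stands. The conflict is between a mandatory and a permissive wording that can be reconciled, and a reader who infers a flat contradiction goes too far. The reconciliation is left to the person classifying, however, and the statement about all defects applies only once a finding has been called a defect.

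A reader might also infer that timing decides which findings are counted, or that classification and timing review are done from one file. The documents do not support this. They say that reports enter the sponsor's safety database under existing practices, and they are silent on who classifies and in what order. The checklist answer on independent review concerns study results generally, in an annex dated 06 March 2014. What can be said is that no safeguard is described.

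A reader might take the 2 to 4 point gap in background rates as the size of the discretion. It is not, for the reason in step 5 of the working. Nor does the plan set a target effect against which to call any shift large.

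Finally, the study is descriptive, and its first objective is to describe the abnormal outcomes. That limits how far a borderline call could stay hidden, but it does not settle the proportion, which is the second co-primary objective.

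**Conclusion.** The point holds in a limited form. Section 9.6.2.2 gives a mandatory and a permissive rule for off-list minor malformations, with no criterion to choose between them, and the result feeds the trimester-stratified risk. The context favours inclusion. No step is described that fixes the defect call before vaccination timing is considered. This is an omission that permits bias, and nothing shows that bias occurred.

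The size is not identifiable from the protocol. Four calls are worth about 1.0 point at 391 infants and 2.0 points at 200, and more in a smaller stratum. These figures rest on the assumed denominators and on an arbitrary count of four. The factor of 1.67 to 2.33 between background rates is an illustrative ceiling on the effect of case definition, not an estimate. The sponsor should make the change because it is cheap and removes the ambiguity whatever its true size.

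**What to change.** 1. In Section 9.6.2.2, change *may be classified* to *are classified* for off-list minor malformations.
2. In each exposure stratum, report two tallies: (a) defects meeting CDC MACDP criteria, for comparison with the rate of about 3%; (b) all morphologic anomalies, including minor ones. Tally (a) aligns the case definition only. The 3% is per live birth, whereas the Registry also counts defects in neonates not delivered alive.
3. Have existing staff record and lock each defect/no-defect call from the outcome description, with vaccination date and trimester withheld. The timing and alternative-cause review in Section 9.7 follows.
4. Keep the *possibility* clause, since it guards against missing a true defect, but flag every case admitted under it and show the risk with and without those cases.

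Because the reports are cumulative and include pregnancies from before 2014, the single rule should also be applied to stored outcome descriptions.

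**Cost.** Protocol wording, a small delay per case and one extra table. No new data are needed. I assume that a case print-out without exposure fields can be produced, which the protocol does not address. Masking may be incomplete where a narrative mentions timing, and it does not mask the reporting healthcare professional who describes the finding.

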9.7. Data analysis (Amended on 05 October 2017)

Pregnancy outcomes include spontaneous abortion (pregnancy loss before 22 weeks gestation), fetal deaths/stillbirths (loss at or after 22 weeks gestation), elective/*induced* abortions and live births. Gestational weeks are counted from the date of the LMP. The second trimester is considered to begin at week 14 and the third trimester begins at week 28. The presence or absence of birth defects or other abnormalities is evaluated within each of the preceding outcome categories.

Pregnancy outcomes are stratified by the trimester of exposure, with an additional stratum for preconception exposure with no subsequent administration of vaccine during pregnancy. Reports of multiple exposures during a pregnancy (i.e., multiple administrations of *Boostrix*) are classified by the earliest trimester of exposure. When exposure occurs before and after conception, the exposure is classified by the dose administered after conception. The calculations of risk for birth defects are made by dividing the number of infants with birth defects by the total number of infants with and without birth defects. ***Given the descriptive nature of this study, confidence intervals will not be calculated.*** The outcomes of the study will be assessed against known rates from an external reference group for the likelihood of a safety signal warranting further investigation.

The majority of spontaneous abortions occur early in pregnancy [Wilcox, 1981; Wilcox, 1983; Elish, 1996]. If spontaneous abortions were to be evaluated as an outcome of interest, it would be essential to enroll pregnancies as soon as possible after vaccination with *Boostrix*. Because enrollment and recognition of pregnancy would occur at various times, it would be virtually impossible to meaningfully evaluate the effects of *Boostrix* on pregnancy loss [Kennedy, 2004]. Therefore, spontaneous abortions without birth defects are excluded from the risk calculations.

The risk in the general population of all birth defects meeting CDC criteria is approximately 3% (1 of 33) of live births [CDC, 2013b]. The estimated risk cited in the medical literature varies because of differences in case definitions, populations sampled and ascertainment methods. The Collaborative Perinatal Project, using a broader case

definition and prospective ascertainment, reports a frequency of 5% to 7% [Chung, 1975]. Most major structural defects originate during the first trimester of pregnancy, which is the critical time for organogenesis [CDC, 2013b]. For such defects, exposures occurring in the second or third trimester are not likely to be causally associated. However, for the sake of completeness and to enable the assessment of possible increases in the frequency of birth defects, all defects will be included in the periodic summary reports of this Registry.

Criteria for review of a specific individual report include:

- Is the timing of the vaccination with *Boostrix* commensurate with the ontogenetic development of the organ(s) affected by the abnormalities?
- Is there another known or likely cause (e.g., pre-existing genetic or chromosomal defect or exposure to a known teratogen)?
- Is the congenital abnormality not previously described (i.e., is it new to medical science)?
- Is there a unique constellation of defects (i.e., is there a new syndrome)?

Criteria for review of aggregate data include:

- Is there a deviation from the expected frequency of all defects indicating an increase in the overall risk of defects?
- Is there a deviation from the expected frequencies of individual defects?
- Is there uniqueness (e.g., a pattern) of the abnormalities that is suggestive of a common etiology?

Studies have shown that the risk of spontaneous abortion is high early in pregnancy and decreases substantially from week 8 to week 28, yielding a cumulative estimated risk of 10% to 22% [Wilcox, 1981; Wilcox, 1983; Wilcox, 1988; Fenster, 1997; Windham, 1997; Khattak, 1999; Anderson, 2000; Osborn, 2000].

While the Registry is to be limited to prospective reports, some pregnancy exposures are reported after pregnancy outcome has been identified (retrospective reports). The Registry will capture retrospective reports, but these reports will not be included in the analyses of prospective reports. In general, retrospective notification of outcomes following exposure to drugs or vaccines is biased toward reporting the severe and unusual cases and is not reflective of the general experience with the drug. Information about the total number of exposed pregnancies, i.e., the pool of exposures from which the retrospective reports arise, is unknown; therefore, incidences of outcomes cannot be calculated from these data. A series of reported birth defects, however, can be analyzed to detect patterns of specific congenital abnormalities and can identify early signals of new vaccine-associated risks. A section of each periodic summary report, separate from the analysis of prospective reports, will describe all abnormal outcomes of retrospectively reported cases.

Exposed pregnancies reported to the Registry before the transition into a PASS (between 03 May 2005 and Q1 2014), from which data were collected and analyzed prospectively, will also be included in the analyses.

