9.1.2. Rationale for study design

This prospective cohort study is designed as a Registry. After market authorization, AEs that occur after administration of the vaccine can and should always be reported. In that case, however, there is no clear group in which the events occur and so a proper rate of occurrence cannot be estimated. In this pregnancy registry, participants are recruited between administration of the vaccine and the potential occurrence of an AE (i.e., a teratogenic effect in the offspring). This allows for a more proper estimation of the rate of occurrence of these events. Nevertheless, the results of this study still need to be regarded with caution as the exact number of women exposed during pregnancy is unknown. Incidences of events can therefore not be calculated from the study data.

Furthermore, it is likely that pregnant women who accept vaccination may differ from those who refuse vaccination in underlying health status, propensity to seek medical care, propensity to report AEs and differences in access to medical care in general. The differential response/participation by vaccinated versus unvaccinated pregnant women in a pregnancy registry could significantly bias risk estimates and possibly in unpredictable ways, because of the inability to collect adequate data to characterize the non-responders. Therefore, the risks of any identified birth defects will be compared to those in the general population, such as that defined by the Metropolitan Atlanta Congenital Defects Program (MACDP).

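### Section 9.7 rules out confidence intervals but compares the birth-defect risk with external rates, so the comparison carries no measure of random error

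*Combined protocol and SAP*

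**What the plan says.** Section 9.7 defines the birth-defect risk as infants with defects divided by all infants, with and without defects. It then states: "Given the descriptive nature of this study, confidence intervals will not be calculated". The sentence after that says the outcomes will be "assessed against known rates from an external reference group for the likelihood of a safety signal" that would merit further investigation.

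Two background figures follow. The general-population risk under CDC criteria "is approximately 3% (1 of 33) of live births", and a study with a broader case definition found 5% to 7%. The first two of the three aggregate review criteria are "Is there a deviation from the expected frequency of all defects indicating an increase in the overall risk of defects" and "Is there a deviation from the expected frequencies of individual defects"; the third concerns patterns of abnormality.

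Section 9.1.2 supports the design in similar terms. Of recruitment between vaccination and outcome it says: "This allows for a more proper estimation of the rate of occurrence of these events". It adds that "the risks of any identified birth defects will be compared to those in the general population". The second co-primary objective (Section 8.1) is itself a proportion: registered pregnancies with any abnormal outcome.

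**The concern.** A purely descriptive study can do without a hypothesis test and a sample size. This plan goes further: it estimates a risk, sets it beside an external rate and asks whether it deviates. That question cannot be answered from a point estimate alone, because the reader cannot tell how far the estimate could have moved by chance.

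The error can run in either direction. A risk somewhat above 3% could be called a signal when it fits chance, and a risk at 3% could be called reassuring when the data also fit a materially higher risk. The individual-defect criterion is the most exposed, since it will often rest on one or two cases.

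The gap concerns the overall birth-defect risk, individual defects and the co-primary proportion. The descriptive co-primary objective, the four case-level criteria and the pattern criterion are not affected. Section 9.7 stratifies outcomes by timing of exposure but does not state an external comparison within each stratum.

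**Working it through.** **1. Is random error covered elsewhere?** No. Section 9.5 sets no minimum sample size. The caution in Section 9.1.2 is about the unknown number of exposed women. Section 9.9 lists biases and leaves the limits of background comparisons to ad hoc discussion in the periodic reports. No test, standard error, observed-to-expected ratio with limits, or numerical signal threshold appears. There is therefore no design figure to reproduce; the only check on the reference is 1/33 = 3.03%, which agrees with the stated 3%.

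**2. Denominators.** The documents count registered pregnancies, not infants with known outcome, so these are assumptions:
- 391: prospective reports from 03 May 2005 to 02 August 2013 (Section 9.2.1.2).
- 196: about half of 391, an assumed loss.
- 991: a ceiling, 391 + 6 × 100, from fewer than 100 registrations a year (Section 9.2.1.2) over the six years to the 2 August 2019 data lock (Section 6).
- 100: an illustrative small denominator.

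**3. Formula.** Exact (Clopper-Pearson) 95% limits for x cases in n infants: lower = the 0.025 quantile of Beta(x, n − x + 1); upper = the 0.975 quantile of Beta(x + 1, n − x).

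**4. Intervals for the overall risk.**

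| Cases / infants | Observed | Exact 95% interval | Multiple of 1/33 |
|---|---|---|---|
| 3 / 100 | 3.0% | 0.6% to 8.5% | 0.21 to 2.81 |
| 6 / 196 | 3.1% | 1.1% to 6.5% | 0.37 to 2.16 |
| 12 / 391 | 3.1% | 1.6% to 5.3% | 0.53 to 1.75 |
| 30 / 991 | 3.0% | 2.1% to 4.3% | 0.68 to 1.42 |
| 24 / 391 | 6.1% | 4.0% to 9.0% | 1.31 to 2.97 |

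The last row shows that a doubling in the pooled data would stand out even at 391.

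**5. Results that fit both reference definitions.** Counts whose interval contains both 1/33 and 5%, the low end of the broader range:
- n = 196: 4 to 11 cases (2.0% to 5.6%).
- n = 391: 12 to 19 cases (3.1% to 4.9%). At the edges, 11/391 has an upper limit of 4.98%, and 20/391 has a lower limit of 3.15%.
- n = 991: 37 to 41 cases (3.7% to 4.1%).

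With 7% in place of 5%, the bands are 7 to 11 cases at 196, 18 to 19 at 391, and none at 991.

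**6. Chance excess.** If the true risk is 1/33, the binomial probability of observing at least 1.5 times that is 19% at n = 100 (5 or more cases), 8.5% at n = 200 (10 or more) and 5.5% at n = 391 (18 or more). In the other direction, 0/100 still has an upper limit of 3.6%, above the reference.

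**7. Individual defects.** One case gives 0.006% to 1.4% at n = 391 (upper/lower = 219) and 0.003% to 0.56% at n = 991 (ratio 220).

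**The case against.** The strongest objection is that an interval would suggest a precision the registry does not have. Reporting is voluntary, and Section 9.1.2 itself concludes that incidences cannot be calculated, so the interval has no clearly defined target population. Systematic error is probably larger: the Registry counts minor anomalies (Section 9.6.2.2), while the 3% figure uses CDC criteria on live births. This stands as a limit on what the interval means. It does not favour a bare point estimate, which carries the same bias and hides the random error as well.

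A second objection is that the omission is deliberate, in a plan with no hypothesis and no sample size, and that the comparison only screens for signals. That justifies having no test. An exact interval is itself a descriptive statistic, and the plan still asks about deviation from expected. A reader could derive the interval if every report gave counts and denominators, but comparison with background is the report's own task.

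Third, the band in step 5 depends on the choice of 5%, and it pairs references with different definitions, a mismatch that no interval resolves. That is fair; with 7% the band narrows sharply. It affects the illustration only, as do the assumed denominators. The roughly 220-fold span is likewise true of any single event at such denominators, and that is why one case needs its interval.

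Fourth, the fix reaches strata and a co-primary proportion for which no external comparison is claimed, and intervals for individual defects picked out for comparison lack nominal coverage. The first two are descriptive additions that do no harm. The selection point is a caveat worth printing with the table.

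**Conclusion.** The point holds and should be fixed. The current text of Section 9.7 excludes intervals and, in the next sentence, plans a comparison that needs them; nothing else in the plan fills the gap.

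The textual finding is certain. Its size depends on the denominators assumed above. It is material for moderate differences in the overall risk at a few hundred infants or fewer, and for individual defects at any denominator considered. It shrinks as the registry grows and does not affect detection of a pooled doubling. Intervals are necessary for the comparison but not sufficient, because they do not measure bias.

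**What to change.** In Section 9.7, replace the sentence on confidence intervals with:

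*Exact (Clopper-Pearson) 95% confidence intervals will be reported as descriptive measures of precision for the birth-defect risk, overall and in each planned exposure stratum, with the overall interval shown beside the external birth-defect reference rates; for the proportion with any abnormal outcome (interval only, no external rate implied); and for any individual defect whose frequency is compared with an expected frequency (observed count, denominator and exact interval). They will not be used as a formal test or signal threshold.*

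The cost is one sentence and a few table columns, with no new data, stratum or design change. The drawback is that readers may take the interval as the whole uncertainty. Each report should state that it covers random error only, that voluntary reporting, loss to follow-up and differences in defect definition may be larger, and that intervals for individual defects selected for comparison do not have nominal coverage.
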